Subjects will be instructed to keep us informed of any medications initiated after their enrollment in the study. Subjects will be reminded of the potential for additive CNS depression resulting from concomitant use of dronabinol and alcohol, opioid analgesics, benzodiazepines, and barbiturates. They will be warned initially of these potential additive effects during the informed consent process. Participants will be warned not to drive, operate machinery, or engage in any hazardous activity while receiving dronabinol. Subjects will also be informed that clonidine may cause drowsiness, dizziness, or lightheadedness associated with orthostatic hypotension. These effects may be worse if taken with alcohol or other medications that can cause drowsiness. Subjects will be warned not to abruptly stop taking clonidine.

Partners Human Subjects Research Application Form

Subjects will also be informed that data on the use of antipsychotic medications and dronabinol and/or clonidine is lacking. Due to the potential for sedation and possible hypotension in subjects taking these medications together, we will monitor carefully for these symptoms while educating subjects about these possible side effects.

- 8.2.1.b. Informed consent. Eligible subjects will complete standard consent documentation. Prior to the volunteer being asked any question about his/her health, the volunteer will be given a consent form to read. The research assistant will go over it in detail with the volunteer. After a physician investigator answers any questions the volunteer may have concerning the study, he/she will be asked to provide their informed consent to the licensed physician investigator. If enrolled in the study, consent to communicate with their other clinicians will be obtained. Clinicians will be notified of their patients' enrollment in the study, thus allowing them to carefully monitor for changes in mood while they are undergoing treatment to stop use of cannabis.
- 8.2.1.c. Randomization. Research staff will stratify subjects according to their self-reported frequency of cannabis use in the past 30 days: 1) daily use; and 2) non-daily use. The stratification procedure will guard against the possibility that one of the experimental conditions (i.e., dronabinol-clonidine or placebo) will be overrepresented by daily users, while non-daily users will predominantly be randomized into the other condition.

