- 8.2.1.d. Availability and Flow of Subjects into Treatment. We plan to screen 50 subjects in the course of 20 months to achieve our desired sample size.
- 8.2.1.e. Study Visits. Following eligibility for the study (as determined by the baseline-1 visit), subjects will come to the laboratory for a baseline-2 visit to complete research assessments, provide a urine sample, and begin daily diaries and Actiwatch (see Section 8.5.2.a.) Subjects will then come to the clinic twice a week during the study medication treatment phase. One visit will include a medical visit (dispensing of pills and Medical Management; see Sections 8.3.1.b, 8.3.2) and research assessments, including a urine screen (see Section 8.5.2.a and Table 8.2). The other visit will consist only of a urine screen (see Section 8.5.2.a). After the 10-week treatment period, participants will have a follow-up assessment visit at 14 weeks. Subjects will also come in once weekly during weeks 11, 12, and 13 following the 10-week treatment period to provide a urine sample, and hand in daily diaries/actiwatch.

Subjects will be randomized to receive either dronabinol and clonidine or placebo. [name] or the research assistants will present 7 day prescriptions to the McLean pharmacy and the subject will receive blister packs containing 1 week of medication or placebo, separated into daily doses. Subjects will be asked to return unused pills at each weekly medical visit; study staff will then perform a pill count for the study record. All groups will receive capsules following the same schedule: 2 capsules three times daily for 10 weeks. Each capsule will contain either dronabinol, clonidine, or placebo. Subjects in the dronabinol-clonidine group will take 5 mg of dronabinol three times daily for 10 weeks (between 7:00-9:00 AM, 3:00-5:00 PM and 9:00-11:00 PM). Subjects in this group will also take clonidine 0.1 mg po bid (between 7:00-9:00 AM and 9:00-11:00 PM) for 8 weeks, followed by a taper to clonidine 0.1 mg po qhs for the last 2 weeks of

Partners Human Subjects Research Application Form

Version Date: July 26, 2016

the protocol. Subjects will be assessed for side effects prior to each dosing increase and the study physician will decide if increasing the dose as scheduled is appropriate. See Table 1 for a schedule of study visits.

Table 1	Cabadula	of Magazinas
i abie i	Scheaule	of Measures

Table 1 Schedule of Measures					
Measure	Baseline 1 and 2	•	_		Week 14

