Describe how risks to subjects are minimized, for example, by using procedures which are consistent with sound research design and which do not unnecessarily expose subjects to risk or by using procedures already being performed on the subject for diagnostic or treatment purposes.

Partners Human Subjects Research Application Form Version Date: July 26, 2016

Care will be taken to minimize risk. In addition to carefully screening prior to enrollment, we have scheduled regular laboratory visits during which we will carefully monitor response to medication or placebo with respect to side effects and changes in mood.

Describe explicitly the methods for ensuring the safety of subjects. Provide objective criteria for removing a subject from the study, for example, objective criteria for worsening disease/lack of improvement and/or unacceptable adverse events. The inclusion of objective drop criteria is especially important in studies designed with placebo control groups.

8.3.1.b. Safety Monitoring.

In order to monitor potential side effects from the initial dose of dronabinol, subjects will be observed at the laboratory facility for 4 hours following the following the first dose of the day in week 1. Subjects will come into the Behavioral Psychopharmacology Research Laboratory for monitoring by a research assistant and a study physician. This observation period is follows the SAMHSA guidelines for induction of buprenorphine, another agonist pharmacotherapy (CSAT 2004). Subjects will remain in the natural settings laboratory for a minimum of 2 hours and a maximum of 6 hours while having vital signs taken every 30 minutes. Subjects will be allowed to leave the facility by cab after being cleared by a study physician. Subjects will be allowed to leave the facility if they have 1) pulse rate greater than or equal to 50 beats per minute or less than or equal to 135 beats per minute; 2) blood pressure less than or equal to 140/90 and greater than or equal to 90/50; and 3) Behavioral Activity Rating Scale (BARS) score of less than 6. If pulse is decreasing, blood pressure is increasing, or BARS is increasing at the 2-hour assessment, the subject will remain an addition 30 minutes until the trend for these parameters is in the correct direction and the subject meets criteria for medical clearance.

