During the 10-week treatment period, subjects will be seen for a MM visit and for urine screen visit. Medication compliance and side effects will be monitored at all visits. The initial visit in week 1 will include a monitored administration of medication described above. Subjects will have follow-up visits at 5, 10 and 14 weeks that will include a urine screen, blood sampling for laboratory testing, as well as evaluation for medication side effects.

Stopping Criteria. New psychotic symptoms thought to be related to dronabinol administration that are present at any pre-dose assessment or that remain present at the end of a 2-hour monitoring period will result in stopping of dronabinol. Clonidine stopping criteria include bradycardia less than or equal to 50 bpm, supine blood pressure of less than or equal to 100/65, a seated blood pressure of less than or equal to 90/60, or orthostatic change of >20 systolic or >10 diastolic on standing, at screening or any pre-dose assessment, or symptoms attributable to low BP (i.e. lightheadedness or dizziness on standing). Adverse events or side effects resulting from administration of either dronabinol or clonidine that persist beyond 7 days will warrant a call to the subjects PCP if they have one, and a decision will be made by the study physician about possible continued participation. If the subject is stopped, they will be followed for follow-up visits only.

Clinically significant lab abnormalities (liver function tests ≥3X normal, for example) will be rechecked immediately and, if determined to be clinically significant by the study

Partners Human Subjects Research Application Form

Version Date: July 26, 2016

physician, the subject will be removed from the protocol and followed for follow-up visits only. Worsening psychotic symptoms that predated study medication will warrant a call to the subject's psychiatrist and possible removal from the protocol if the patient is thought to be unstable by either the outpatient psychiatrist or the study physician. Similarly, suicidal ideation will warrant contact with the outpatient psychiatrist and possible removal from the protocol. Suicidal ideation with a plan will result in immediate removal from the protocol and the subject will be escorted by staff to the Psychiatric Emergency Room.

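### First-dose discharge rule: the printed pulse limit excludes no one, falling pressure triggers no hold, and the floor touches the clonidine stopping values

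*Combined protocol and SAP*

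**What the plan says.** Section 8.3.1.b (Safety Monitoring) describes observation after the first dose of the day in week 1, with vital signs every 30 minutes and clearance by a study physician. Three conditions allow a subject to leave:

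- Pulse: "pulse rate greater than or equal to 50 beats per minute or less than or equal to 135 beats per minute".
- Pressure: "blood pressure less than or equal to 140/90 and greater than or equal to 90/50". No body position is given.
- A Behavioral Activity Rating Scale (BARS) score below 6.

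A trend rule follows: "If pulse is decreasing, blood pressure is increasing, or BARS is increasing at the 2-hour assessment, the subject will remain an addition 30 minutes". The hold lasts until the trends run in what the text calls the correct direction, which it does not define, and the clearance conditions are met.

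The Stopping Criteria paragraph gives the clonidine limits: "Clonidine stopping criteria include bradycardia less than or equal to 50 bpm, supine blood pressure of less than or equal to 100/65", then "a seated blood pressure of less than or equal to 90/60", an orthostatic change of more than 20 systolic or 10 diastolic, or symptoms of low pressure. The numeric values are tied to screening or a pre-dose assessment. Section 9.4, exclusion criterion 9, repeats the same list.

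On hazards, the Study Restrictions text warns that "clonidine may cause drowsiness, dizziness, or lightheadedness associated with orthostatic hypotension" and refers to possible hypotension when the study drugs are taken with antipsychotics. Section 8.3.1.c has staff ask about orthostatic symptoms at each medical visit. Foreseeable Risks repeats the clonidine warning.

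**The concern.** The discharge rule is the only numeric check on pulse and pressure that the protocol attaches to the period after the first dose. Three features of its wording do not do what such a check is for.

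The pulse condition, read literally, screens out nobody. The trend rule reacts to a pressure rise and is silent on a fall, while every pressure hazard named elsewhere is low pressure. The floor for discharge sits at or below values the protocol treats elsewhere as reasons to stop or exclude, and discharge carries no orthostatic or symptom condition although the stopping list has both.

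At stake is whether staff following the text would release a subject whose pressure is falling towards the protocol's own limits, and whether they can tell which limit applies to the reading in front of them.

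**Working it through.** The plan gives no figure to reproduce. The check sets the rules side by side on whole-number values.

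**1. Pulse (8.3.1.b against Stopping Criteria).** Discharge as printed needs P ≥ 50 *or* P ≤ 135. It fails only if P < 50 and P > 135 together, which is impossible. Over 30 to 160 bpm, no value fails. All 21 values from 30 to 50 meet the stopping limit of 50 or less and also pass the discharge test. If *and* is substituted, discharge becomes 50 ≤ P ≤ 135, and the overlap with P ≤ 50 is the single value 50.

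**2. Seated pressure (8.3.1.b against Stopping Criteria and criterion 9).** The dischargeable region is systolic 90–140 and diastolic 50–90. That is 51 × 41 = 2,091 pairs, or 2,090 after dropping 90/90, where systolic does not exceed diastolic. The seated stopping limit is 90/60 or less, and the text does not say whether both components must be low.

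| Reading of 90/60 or less | Overlap with dischargeable values |
|---|---|
| Both components low | systolic 90, diastolic 50–60: 11 pairs |
| Either component low | (51 × 11) + 29 = 561 + 29 = 590 pairs; 590/2,090 = 28% |

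The 29 are the pairs with systolic 90 and diastolic 61–89. The 28% is a share of grid cells, not of patients. How many subjects would have such readings cannot be derived from the documents.

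**3. Trend.** Take two illustrative subjects whose pulse and BARS do not trigger a hold.

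- Pressure falls from 110/70 to 90/55: the final value meets the discharge condition, and no trend limb is triggered.
- Pressure rises from 100/65 to 115/75: the final value also meets the discharge condition, but the rising limb holds the subject for a further 30 minutes.

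The pulse limb differs: holding on a decreasing pulse is consistent with the bradycardia criterion.

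**4. Timing.** The numeric clonidine limits apply at screening or before a dose, whereas discharge uses a reading after a dose. The Stopping Criteria link the dronabinol rule on new psychotic symptoms to the end of a 2-hour monitoring period, but give the clonidine vital signs no such link. Section 8.3.1.c refers to exclusionary pressure criteria at medical visits without saying whether the reading is pre-dose. The documents therefore leave open whether the stopping values govern the post-dose reading.

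**The case against.** A reader might infer that the protocol sends subjects home while they meet its own clonidine stopping rule. The documents do not support that. The numeric values are tied to screening or a pre-dose assessment, so a post-dose 90/55 does not trigger them as written. A study physician must clear each subject, vital signs are taken every 30 minutes, and low-pressure symptoms form a separate limb of the stopping list that, as punctuated, is not clearly confined to pre-dose readings.

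The observation's stated purpose is dronabinol side effects, and Foreseeable Risks lists fast heart rate among the cannabinoid effects. A rising pressure also matters for the 140/90 ceiling. Because the correct direction is undefined, saying that the plan calls falling pressure correct would be an inference; the text shows only that a fall does not trigger a hold. The *or* is very probably a slip, since the pressure item beside it uses *and*.

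Two tempting measures of size also fail. The supine limit of 100/65 would enlarge the overlap, but Table 1, footnote c, schedules sitting and standing readings only. One could also note that "the subject will receive blister packs containing 1 week of medication or placebo" and count 2 × 7 = 14 clonidine doses, 13 of them after the observed one. That assumes full twice-daily dosing from the observed dose, and it measures exposure in any subject rather than how often the overlap occurs.

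These points narrow the finding but do not remove it. Physician judgement does not make a vacuous limit bind. A probable slip in operative safety text still needs correcting. Dronabinol and clonidine share the 7:00–9:00 AM dosing window (Section 8.2.1.e), so the stated dronabinol purpose does not make clonidine's pressure effects irrelevant.

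**Conclusion.** The concern holds in a limited form.

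- **Pulse:** wrong as written. No pulse fails the discharge test.
- **Trend:** a fall in pressure triggers no hold, although low pressure is the only pressure hazard the documents name. The pulse limb of the same rule is consistent with the stopping criteria.
- **Limits:** the floor reaches the stopping and exclusion values. On the narrow reading the overlap is an edge: systolic 90 with diastolic 50–60, and pulse exactly 50. It widens if either pressure component suffices, or if the printed *or* is applied.

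This rests on treating the seated limit as the relevant one, because discharge posture is unstated and sitting is a scheduled position. The two rules act at different times, so this is a mismatch to reconcile and not proof that subjects meeting the stopping rule are released. Severity is minor to moderate: the defect lies in an operative safety rule, its frequency is unknown, and physician clearance mitigates it.

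**What to change.** Reword the pulse condition in Section 8.3.1.b so that both of its limits bind. Then reconcile that section with the Stopping Criteria and with exclusion criterion 9 on:

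1. the discharge limits for pulse and pressure, including whether one or both pressure components must be low;
2. the body position of the discharge reading, and whether orthostatic change and low-pressure symptoms count at discharge;
3. whether the clonidine stopping values apply to the post-dose reading;
4. the direction of the pressure trend that prompts a hold, with the correct direction defined for each parameter.

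Which values and which direction apply is a clinical decision for the sponsor. The cost is protocol wording; no new measurements are needed.

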Subjects who experience uncomfortable side effects (e.g., drowsiness or vertigo) may have their dose lowered from 2 capsules three times a day to 2 capsules twice daily by eliminating the middle dose of the day; a subject receiving active medication, for example, could then have a dronabinol dose reduction to 10 mg of dronabinol daily. If this leads to fewer side effects, the study physician will ask if the subject is willing to try the full dose again. If not, or if the subject tries the full dose again and is unable to tolerate it, the subject will be maintained on the lower dose. If a subject cannot tolerate 2 capsules twice per day, the medication will be discontinued, and the subject will be tapered off of the Clonidine, but the subject will continue to be followed for research visits. Similarly, we will monitor for potential cardiovascular side effects resulting from clonidine pharmacotherapy. At each medical management visit, we will assess vital signs and ask the subject about symptoms of orthostatic hypotension, such as dizziness when rising to stand from a seated position, blurry vision, or weakness. If subjects describe these symptoms without meeting exclusionary blood pressure criteria, we will hold the third set of capsules to see if this leads to fewer side effects, the study physician will ask if the subject is willing to try the full dose again. If not, or if the subject tries the full dose again and is unable to tolerate

Partners Human Subjects Research Application Form

Version Date: July 26, 2016

it, the subject will be maintained on the lower dose. If a subject cannot tolerate 2 capsules twice per day, the medication will be discontinued, but the subject will continue to be followed for research visits.

8.3.2. Medical Management Visits.

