8.5.2.a. Urine Screens. The primary outcome measure will be cannabis use, as measured by twice-weekly quantitative urine screens during treatment. Quantative urine screens will also be measured during weeks 11, 12, 13, and 14 following the 10-week treatment period. Cannabis is a particularly challenging drug of abuse for measuring outcome because of the false-positive urine screens that can occur as the result of long-term accumulation of cannabis metabolites. In an attempt to avoid false-positive results, we will obtain 2 supervised urine samples weekly: 1 at the medical visit and 1 on another day, ordinarily with 3-4 days separation from the clinical visits (e.g., Monday-Thursday, Tuesday-Friday, or Monday-Friday); this should maximize the time frame covered by our urine screens. We will send the urine samples to Quest Diagnostics Laboratory (Cambridge, MA, a NIDA-certified laboratory), where the urines

Partners Human Subjects Research Application Form Version Date: July 26, 2016

will be screened by immunoassay for the THC metabolite 11-nor-carboxy-∆ 9tetrahydrocannabinol (THC-COOH) as well as other drugs of abuse. Urine creatinine concentrations will also be measured to assess urine concentration. The threshold for detection of THC-COOH will be 20 ng/ml. Samples positive for this metabolite will undergo further analysis by gas chromatography-mass spectroscopy to obtain quantitative THC-COOH concentration; we will then calculate the ratio of this metabolite to urine creatinine concentration. We will adopt the method of Heustis and Cone (1998) to differentiate new marijuana use from residual drug excretion as a result of previous use; these recommendations are based on their controlled clinical studies of urinary excretion profiles of creatinine and marijuana metabolites following marijuana administration in humans. We will label a urine negative (i.e., abstinent from cannabis) if 1) the ratio of THC-COOH to creatinine in the urine does not increase by >50% from the ratio obtained in the previous urine screen, and 2) the subject also reports using no cannabis since the previous urine test.

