All data collected will be de-identified with subject ID numbers and used for research purposes only. Written records will be kept in a locked file cabinet in a locked office. They will be destroyed after 5 years. Computerized data files will also be de-identified with subject ID numbers and kept in a password protected file on a password protected computer.

8.9. Statistical Analysis

The primary data analysis will be an intent-to-treat analysis, which includes all randomized subjects. Of note, every attempt will be made to continue assessing subjects even if they drop out of treatment. In addition, we will replicate all analyses with the completers only. The primary and secondary outcome variables are intended to

Partners Human Subjects Research Application Form Version Date: July 26, 2016

explore various aspects of response to therapy and to help define a clinically meaningful response. The primary outcome measures, Actiwatch-scores, daily diaries, TLFB self-report data, in addition to quantitative urinary THC metabolites, have been chosen for their ability to indicate daily use of cannabis by relying on self-report of use.

Specifically, for assessing the effect of dronabinol and clonidine on cannabis use patterns, we propose to use the generalized estimating equations (GEE) approach to longitudinal analysis, appropriately accounting for the positive correlation among repeated urine screen assessments within the same individual.

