Describe the plan for monitoring the data to ensure the safety of subjects. The plan should include a brief description of (1) the safety and/or efficacy data that will be reviewed; (2) the planned frequency of review; and (3) who will be responsible for this review and for determining whether the research should be altered or stopped. Include a brief description of any stopping rules for the study, when appropriate. Depending upon the risk, size and complexity of the study, the investigator, an expert group, an independent Data and Safety Monitoring Board (DSMB) or others might be assigned primary responsibility for this monitoring activity.

NOTE: Regardless of data and safety monitoring plans by the sponsor or others, the principal investigator is ultimately responsible for protecting the rights, safety, and welfare of subjects under his/her care.

Safety Monitoring. Dronabinol and clonidine both have been shown to have favorable safety profiles; they have been well-tolerated in several clinical trials and few adverse events have been reported. Nonetheless, we will monitor safety through the standardized methods described above in the MM visits. We will have a low threshold for obtaining additional medical workup during the study if the subject reports medical symptoms. If a subject has a clinically significant laboratory or other medical abnormality that cannot be attributed to another cause, the subject's medication will be discontinued and the subject will be followed for research visits.

As discussed above in Section 8.2.i.a, the study physician will perform a physical examination and obtain an ECG at baseline and at 24 weeks. Laboratory data (urinalysis, blood chemistries, complete blood count, electrolytes, and liver function tests) will be done at baseline and 5, 10, and 14 weeks as well. Women of childbearing potential will have urine pregnancy tests at 4, 8, and 14 weeks during the study; women who become pregnant will have their medication discontinued and will be referred to an obstetrician; like all subjects, they will still be followed for research visits.

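### Subjects stopped for persistent side effects or laboratory abnormalities drop to visits at weeks 5, 10 and 14, losing most urine screens still due and conflicting with other sections and the intent-to-treat commitment

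*Combined protocol and SAP*

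**What the plan says.** Section 8.3.1.b, under Stopping Criteria, has two routes that end in reduced follow-up. For adverse events or side effects lasting more than 7 days, the study physician decides on continued participation, and then: "If the subject is stopped, they will be followed for follow-up visits only". For a laboratory abnormality, the rule applies if it is judged clinically significant by the study "physician, the subject will be removed from the protocol and followed for follow-up visits only". The same section fixes when those visits fall: "Subjects will have follow-up visits at 5, 10 and 14 weeks that will include a urine screen".

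Other sections read differently:

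- Data and Safety Monitoring, for a clinically significant laboratory or other medical abnormality with no other cause: "the subject's medication will be discontinued and the subject will be followed for research visits".
- Section 8.3.1.c (Dose Adjustment), for a subject who cannot tolerate the reduced capsule schedule: "the medication will be discontinued, but the subject will continue to be followed for research visits".
- Section 8.2.1.a (Safety Monitoring) keeps research visits for women who become pregnant and says this is how all subjects are treated.
- Section 8.9 plans an intent-to-treat analysis of everyone randomized and adds that "every attempt will be made to continue assessing subjects even if they drop out of treatment".

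On the outcome, section 8.5.2.a states: "The primary outcome measure will be cannabis use, as measured by twice-weekly quantitative urine screens during treatment". Section 8.2.1.e sets the matching schedule: "Subjects will then come to the clinic twice a week during the study medication treatment phase".

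**The concern.** Staff cannot follow both instructions after a clinically significant laboratory abnormality. If they follow section 8.3.1.b, the twice-weekly urines and the weekly craving and withdrawal measures fall to three visits from the moment of stopping. An intent-to-treat comparison needs exactly those later observations.

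The screens that remain also change in meaning. Section 8.5.2.a labels a urine negative only if the metabolite-to-creatinine ratio has not risen by more than 50% since the preceding screen and the subject reports no use since then. Screens are ordinarily planned 3-4 days apart. Under the reduced schedule the interval can reach about 5 weeks.

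Section 8.9 proposes GEE and gives no rule for missing screens. Ordinary GEE relies on data missing completely at random, which data missing because of a safety event may not satisfy. Since the two routes concern effects of dronabinol or clonidine, the loss could also differ between arms.

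**Working it through.** **Check of the schedule against the plan's own figures.** The stated payment total reproduces with three follow-up visits, ten non-MM urine visits and three visits in weeks 11-13: 50 + 25 + 3×50 + 5×25 + 5×30 + 50 + 3×30 + 100 = $740. Half of 18 subjects is 9 per arm, and 9 × 0.80 = 7.2 agrees with the 7-8 expected to be exposed to dronabinol (section 8.2). The document gives no power calculation, effect size or stopping rate by arm.

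**Screens per subject.** Planned: 2 × 10 = 20 during treatment, plus 4 in weeks 11-14, giving 24. For a stop at the end of week w, let k be the number of weeks 5 and 10 still to come, with one urine at each.

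- Obtained = 2w + k
- Lost = 20 − 2w − k
- Still due at stopping = 20 − 2w

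| Stop, end of week | Obtained of 20 | Lost | Still due | Lost, share of those due |
|---|---|---|---|---|
| 1 | 4 | 16 | 18 | 89% |
| 2 | 6 | 14 | 16 | 88% |
| 3 | 8 | 12 | 14 | 86% |
| 4 | 10 | 10 | 12 | 83% |
| 5 | 11 | 9 | 10 | 90% |
| 6 | 13 | 7 | 8 | 88% |
| 7 | 15 | 5 | 6 | 83% |
| 8 | 17 | 3 | 4 | 75% |
| 9 | 19 | 1 | 2 | 50% |

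A stop at week 2 also keeps only the week-14 screen of the four after treatment, so 7 of 24 overall. The weekly craving and withdrawal measures fall to 2 + 2 = 4 of 10 during treatment.

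**One arm.** Planned: 9 × 20 = 180. With 1, 2 or 3 subjects stopped at week 2, the loss is 14, 28 or 42 screens (7.8%, 15.6% or 23.3%).

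**Illustration of the effect on the estimate.** Assumptions, none from the document: 50% of screens positive on drug, 90% after stopping, m of 9 active subjects stopped at the end of week 2, no placebo subject stopped.

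- All planned screens: [(9 − m)×20×0.5 + m×(4×0.5 + 16×0.9)] / 180 = (90 + 6.4m)/180
- Observed, samples pooled: [(9 − m)×20×0.5 + m×(4×0.5 + 2×0.9)] / [(9 − m)×20 + 6m] = (90 − 6.2m)/(180 − 14m)
- Observed, subjects weighted equally: [(9 − m)×0.5 + m×(3.8/6)] / 9

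| m | All planned | Pooled | Gap (points) | Equal weight | Gap (points) |
|---|---|---|---|---|---|
| 1 | 53.6% | 50.5% | 3.1 | 51.5% | 2.1 |
| 2 | 57.1% | 51.1% | 6.1 | 53.0% | 4.1 |
| 3 | 60.7% | 51.7% | 8.9 | 54.4% | 6.2 |

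**Effect of the longer label interval.** Keep true positivity at 50% throughout, let m = 2, and suppose that all four retained screens are labelled positive because the look-back is so long. The pooled rate is then (7×10 + 2×(2 + 2))/152 = 78/152 = 51.3% against 50%. This error runs against the active arm.

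**The case against.** Much can be said for the plan. Section 8.9 already states the intent-to-treat aim and continued assessment, and section 8.3.1.c keeps research visits for ordinary intolerance. Sections 8.2.1.a, 8.3.1.c and 8.9 speak of stopping medication or dropping out of treatment, whereas section 8.3.1.b speaks of participation and removal from the protocol. These are not plainly the same event. The term research visits is never defined, and no section says outright that twice-weekly urines continue after stopping. Measures are thinned rather than ended: Table 1 keeps urine, craving, withdrawal and use inventory at weeks 5, 10 and 14, and diary pages carry prepaid postage. This is also an 18-subject pilot whose outcomes are described as exploratory.

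Those points limit the scope, but they do not remove the direct conflict over laboratory abnormalities or the inconsistency with section 8.2.1.a, which extends continued research visits to all subjects.

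Two stronger readings are tempting. A reader might infer that every safety trigger leads to the reduced schedule. The text does not say so: new psychotic symptoms stop dronabinol, and the pulse and blood-pressure limits are criteria for stopping clonidine, with no clear visit rule attached to either. A reader might also infer that the loss falls mainly on the active arm and flatters it. The rules are applied blind, placebo subjects can meet them too, and no rates by arm are given. The direction of any bias is likewise open. It depends on use after stopping and on the label interval. Because dronabinol is THC and the assay measures a THC metabolite, stopping it may also shift the ratio without any change in cannabis use.

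**Conclusion.** The point holds for two routes: side effects persisting beyond 7 days and clinically significant laboratory abnormalities. Section 8.3.1.b conflicts directly with Data and Safety Monitoring on the second, and is inconsistent with sections 8.2.1.a, 8.3.1.c and 8.9 more generally.

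The loss of data follows from the schedule alone. For stops from week 1 through week 8, most of the treatment-period screens still due are lost. More than half of the full 20 are lost only if the stop comes by the end of week 3. This takes follow-up visits to mean weeks 5, 10 and 14, as section 8.3.1.b and the payment schedule do. Sections 8.1 and 8.2.1.e use the term for week 14 alone, which would make the loss larger.

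Unequal loss between arms is a plausible inference, not a documented fact. The gaps of about 3 to 9 points (pooled) or 2 to 6 points (equal weights) rest wholly on assumed rates, on no placebo stops, and on simple averages in place of the planned GEE. They show what could happen and do not estimate a bias. The wording should be fixed; in a pilot with no stated decision threshold, the point does not go further than that.

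**What to change.** Reconcile section 8.3.1.b with sections 8.2.1.a, 8.3.1.c, 8.9 and Data and Safety Monitoring by separating the end of study medication from the end of outcome collection. Both sentences in section 8.3.1.b need rewording, including the phrase about removal from the protocol, which would otherwise clash with continued visits. The new text could say that subjects whose medication is stopped are asked, if willing and clinically able, to continue the scheduled urine screens and weekly research assessments through week 14. It should also define research visits and follow-up visits once. Section 8.3.1.b states no visit schedule after removal for worsening psychosis or suicidal ideation, and the same edit can supply one. When, why and for whom treatment stops is left unchanged.

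The cost is one wording amendment. The visits and payments are already in the plan for every subject, so the $740 maximum does not rise; the document gives no assay budget to check. The downside is visit burden for subjects off medication, some of whom may decline. Some screens will therefore still be missing, and the rewording does not replace a statement in section 8.9 of how missing screens are handled.
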